	Appendix 4 Prohibited Concomitant Medications	
	Appendix 5 Scoring Atopic Dermatitis (SCORAD)	
	Appendix 6 Pruritus NRS assessment	
	Appendix 7 DLQI Questionnaire	

List of Abbreviations

AD Atopic Dermatitis
AUC Area Under the Curve

β-hCG Beta-human Chorionic Gonadotropin

CI Confidence Intervals

Cmax Maximal Plasma Concentration

CRF Case Report Form CRP C-Reactive Protein

DLQI Dermatology Life Quality Index

EW Early Withdrawal ECG Electrocardiogram

EMA European Drug Administration
EASI Eczema Area and Severity Index
eCRF Electronic Case Report Form
FDA U.S. Food & Drug Administration
FSH Follicle-Stimulating Hormone

FVC Force Vital Capacity
GCP Good Clinical Practice
GFR Glomerular Filtration Rate
IB Investigator's Brochure

IL Interleukin

IGA Investigator's Global Assessment

JAK Janus kinase

IEC Independent Ethics Committee

IFN-γ
 Interferon- gamma
 IgE
 Immunoglobulin E
 IgM
 Immunoglobulin M
 IND
 Investigational New Drug
 IRB
 Independent Review Board

ITT Intention-to-Treat

IVRS Interactive Voice Response System

IUDIntra-Uterine DeviceLDHLactic Dehydrogenase

LLoQ Lower Limit of Quantification

Mcg Micrograms

MedRA Medical Dictionary for Regulatory Activities

NRS Numeric Rating Score
PK Pharmacokinetics
PP Per Protocol

PPD Purified Protein Derivatives
QD Quaque Die (Once Daily)
Plantagia Authorities

RA Rheumatoid Arthritis

RAP Reporting and Analysis Plan

SAE severe adverse event
SAP Statistical Analysis Plan

Reistone Biopharma	Confidential	RSJ10303
SD	Standard Deviation	
SPM	Study Procedures Manual	
SCORAD	Scoring of Atopic Dermatitis	

TCS

Scoring of Atopic Dermatitis
Topical corticosteroids
Time of last quantifiable concentration
Upper Limit of Normal Tlast

ULN

1. Protocol Summary

Atopic Dermatitis (AD) is a common chronic inflammatory skin disease characterized by recurrent, pleomorphic skin lesions, dry skin, and severe pruritus. Atopic dermatitis usually begins in infancy or in children and is chronic, while severe cases may persist in adulthood. Meanwhile, some adult cases develop in adulthood. In most countries worldwide, atopic dermatitis has a prevalence of 10% - 20% in children and 2 - 8% in adults 1 . Moderate to severe atopic dermatitis has been reported in about 20% of cases 2 . In China, the prevalence of atopic dermatitis has also increased rapidly over 20 years 3 . As reported in 2016, the overall prevalence of atopic dermatitis in China is

7.8%⁴. As a chronic relapsing inflammatory disease, atopic dermatitis is not curable at present, and the treatment for moderate to severe AD is difficult.

Janus Kinase (JAK) - Signal transducers and activators of transcription (STAT) signaling pathway as an important intracellular signal transduction pathway plays a critical role for signal transduction from cell membrane to nucleus by various cytokines such as interleukin (IL), interferon (IFN) and other molecules. Inflammatory mediators that depend on the JAK/STAT pathway are involved in the pathogenesis of many inflammatory diseases. Therefore, JAK inhibitors have become a research hotspot in the treatment of immune-mediated inflammatory diseases. There are a number of JAK inhibitors currently under investigation for the treatments of immune-induced disease, such as rheumatoid arthritis (RA), psoriatic arthritis, psoriasis, ulcerative colitis (UC), Crohn's disease (CD), ankylosing spondylitis. Meanwhile, more and more case reports and early Clinical studies have suggested that JAK inhibitors have also achieved good results in the treatment of inflammatory skin diseases such as atopic dermatitis, alopecia areata, psoriasis, and vitiligo.

Compared with traditional immunosuppressants, JAK inhibitors are more targeted. As a small-molecular oral formulation, JAK inhibitors are more convenient and more acceptable to patients than biologics administered by injection. Another advantage of these JAK inhibitors is that they reduce the risk of inadequate responses due to immunogenicity. SHR0302 is a highly selective JAK1 inhibitor. An *in vitro* study has demonstrated that its selectivity to JAK1 compared to JAK2 is about 16 times more than tofacitinib and baricitinib. The high selectivity of SHR0302 to JAK1 also makes it a favorable candidate from a benefit risk safety perspective.

This proposed study is a randomized, double-blind, placebo-controlled, 3-arm parallel, multicenter phase II study, which designed to explore the efficacy and safety of SHR0302 treatment for patient with moderate to severe atopic dermatitis. This study will be conducted over a 12-week treatment period. Two active doses of SHR0302 will be compared to placebo and improvement in atopic dermatitis will be assessed using the Investigator's Global Score (IGA). IGA response is defined as IGA achieving 0 (clear)/1 (almost clear) and an improvement in IGA of \geq 2 from baseline (as the primary endpoint at week 12), which is widely endorsed by clinical and regulatory authorities. Improvement in eczema area and severity index (EASI) and scoring atopic dermatitis (SCORAD) are also very important and established as secondary endpoints.

1.1 Study objectives and endpoints

The objective is to evaluate the efficacy and safety of SHR0302 4 mg QD and 8 mg QD treatment for adult subjects with moderate to severe atopic dermatitis.

Primary objective	Primary endpoint	
To evaluate the efficacy of SHR0302 4 mg QD, 8 mg QD compared to placebo in adult subjects with moderate to severe atopic dermatitis at Week 12	• The percentage of subjects achieving IGA response at Week 12. IGA response is defined as IGA 0/1 (clear/almost clear) together with IGA improvement ≥ 2 from baseline.	
Secondary objective	Secondary endpoints	
To evaluate safety and tolerability of oral SHR0302 in subjects with moderate to severe atopic dermatitis	 To assess safety and tolerability by laboratory parameters To assess safety and tolerability by collection of AE/SAE incidence 	
	To measure vital signs (blood pressure, heart rate, body temperature and respiratory rate)	
	To measure subjects' total lipid profile, including triglycerides, low-density lipoprotein (LDL), and high-density lipoprotein (HDL)	
	 To measure subjects' thyroid profile: TSH, free T4 and free T3 To evaluate liver and renal function 	
	• 12-lead ECG	

To evaluate the other efficacy endpoints and patient reported outcome of SHR0302 in adult subjects with moderate to severe atopic dermatitis	 Percentage of EASI change from baseline at Weeks 1, 4, 8, and 12 Percentage of Subjects Achieving IGA Response at Weeks 1, 4, 8 Percentage of Subjects With ≥ 50%, 75%, and 90% EASI improvement from baseline (EASI50, EASI75, EASI90) at Weeks 1, 4, 8, and 12
	• Change from baseline in SCORAD at Weeks 1, 4, 8, and 12
	 Percentage of Subjects With ≥ 50%, 75%, and 90% SCORAD improvement from baseline (SCORAD50, SCORAD75, SCORAD90) at Weeks 1, 4, 8, and 12
	 Percent of pruritus numerical rating scale (NRS) change from baseline at Weeks 1, 4, 8, and 12
	 Percentage of Subjects Achieving Pruritus NRS improvement ≥3 from Baseline in at Weeks 1, 4, 8, and 12
	• Change from baseline in Dermatology Life Quality Index (DLQI) at Weeks 1, 4, 8, and 12
	• Change from baseline in biomarker IgE at weeks 1, 4, 8 and 12
To explore Pharmacokinetic and dose-response properties of SHR0302 in subjects with moderate to severe atopic dermatitis.	 Systemic exposure of SHR0302 at steady state in subjects with atopic dermatitis (ie: concentration and area under the curve)

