3.1.2 Secondary objectives

- To evaluate the safety and tolerability of oral SHR0302 in subjects with moderate to severe atopic dermatitis.
- To evaluate the impact of oral SHR0302 on other efficacy endpoints in subjects with moderate to severe atopic dermatitis and on the reported outcomes of subjects.

- To investigate the pharmacokinetic (PK) characteristics of SHR0302 in subjects with moderate to severe atopic dermatitis, and to explore the exposure-effect relationship.

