5.2 FINAL ANALYSIS

The PK statistical analysis plan will not be included here as it will be described in a separate document.

The final analysis specified in this SAP will be performed after the database locked and the data released.

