14.1 OVERVIEW OF EFFICACY ANALYSES

The following hypotheses will be tested based on the primary endpoint and objective:

- H_{01} : Percentage of subjects achieving an IGA response in the SHR0302 8 mg QD dose group at Week 12 - Percentage of subjects achieving an IGA response in the placebo group at Week12 = 0;
- H_{11} : Percentage of subjects achieving an IGA response at Week 12 in the SHR0302 8 mg QD dose group - Percentage of subjects achieving an IGA response at Week 12 in the placebo group $\neq 0$.
- H_{02} : Percentage of subjects achieving an IGA response in the SHR0302 4 mg QD dose group at Week 12 - Percentage of subjects achieving an IGA response in the placebo group at Week12 = 0;
- H_{12} : Percentage of subjects achieving an IGA response at Week 12 in the SHR0302 4 mg QD dose group - Percentage of subjects achieving an IGA response at Week 12 in the placebo group $\neq 0$.

By using the Hochberg¹ incremental procedure, the type I error for the primary endpoint will be controlled at the level of 0.1 bilaterally. Two p-values will be gained and sorted ($p_{(2)} \geq p_{(1)}$). Then start with the least significant comparison ($p_{(2)}$) and continue as long as the test is not significant until the first time when a significant comparison occurs, and all remaining hypotheses will be rejected. The decision rules are provided in below figure 2.

[figure not shown]

Figure 2 The decision rules of hypothesis

NOTE: $H_{(01)}$ is the corresponding null hypothesis of the smallest p value $p(1)$

Analyses of secondary efficacy and other analyses will be provided for comparison 4 mg QD and 8 mg QD versus placebo, respectively.

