14.2 PRIMARY EFFICACY ANALYSIS

Analysis of the primary efficacy endpoint will be based on FAS.

The primary efficacy endpoint for this study is the percentage of subjects achieving IGA response at Week 12. IGA is the investigator's global assessment of the subject's general condition and consists of a 6-point severity scale from clear to very severe disease ("complete clearance", "almost

complete clearance", "mild", "moderate", "severe", and "very severe"). IGA response is defined as IGA score of 0/1 (complete or almost complete clearance of skin lesions) with an improvement in IGA score by ≥ 2 from baseline.

Subjects who early withdraw from the study for any reason will be considered as non-responders at each post-withdrawal assessment time point. Descriptive summaries of the primary efficacy endpoint will be based on non-missing data only.

Due to the impact of the COVID-2019 pandemic, subjects may have their primary efficacy endpoint assessed outside the scheduled time window of visit 6. If the primary efficacy endpoint is missing within the planned time window (between study days 82 and 88), it will be considered to impute with results of assessment within 89 to 102 study day (ie, extended visit).

The method of normal approximation to binomial will be used to test whether each active drug group is superior to the placebo group. Estimation of the difference and its 90% confidence interval between each drug group and the placebo group, as well as the corresponding p value for test will be provided.

Referenced SAS code:

```
PROC FREQ DATA = adam.adeff;  
  TABLE treat*aval/CHISQ RISKDIFF (CL = WALD) ALPHA = 0.1;  
  RUN;
```

In the above codes, variables are defined as follows:

Aval = IGA response at Week12

Treat = treatment group

In addition, IGA response and its 90% confidence interval at Week 12 will also be provided for each treatment group.

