A mixed-effects repeated measures model (MMRM) will be used to analyze percentage of EASI change from baseline including treatment group, baseline value, visit, and treatment-by-visit interaction as fixed effect and visit as repeated variable. An unstructured covariance matrix will be used to model the within-subject variance-covariance errors. If model fails to converge, the following options will be considered in order until convergence achieved: TOEPH (Heterogeneous Toeplitz) 、 AR(1)(Heterogeneous autoregressive) 、 TOEP(Toeplitz) and CS (Compound symmetry). The Kenward-Roger approximation will be used to estimate the degrees of freedom. The comparisons of interest will be the contrasts between each active dose and placebo at every time point. For the treatment difference of each active dose versus placebo at each visit, the model estimated least square means, standard error, p-value, and two-sided 90% confidence interval will be reported.

Referenced MMRM SAS code:

```
PROC MIXED DATA=adam.adeff METHOD=REML;  
  CLASS treat visit subj;  
  MODEL chgEASI= treat visit treat*visit basval /SOLUTION DDFM=KR;  
  REPEATED visit/SUBJECT=subj TYPE=UN;  
  LSMEANS treat*visit/DIFF PDIFF CL;  
  RUN;
```

In the above code, variables are defined as follows:

ChgEASI = change from baseline in EASI for each visit

Treat = treatment group

Visit = visit

Subj = subject

Basval = baseline EASI score

Least square means of change from baseline in EASI score at each assessment visit will be graphically displayed for each treatment using a line plot.

EASI score and change from baseline will be summarized by treatment at each efficacy assessment visit, and statistics including mean, standard deviation, and 90% confidence interval will be provided. Same statistics will also be provided for each site score as well as for the four symptoms.

14.3.3 Percentage of subjects with $\geq 50\%$, 75% , and 90% EASI improvement from baseline (EASI50, EASI75, EASI90) at Weeks 1, 4, 8, and 12

Percentage of EASI change from baseline will also be derived as a dichotomous result according to the following three criteria: $\geq 50\%$ (EASI50), $\geq 75\%$ (EASI75), and $\geq 90\%$ (EASI90). For each derived dichotomous EASI result, the comparison between 4 mg QD and 8 mg QD versus placebo will be performed by method of normal approximation to binomial or Fisher's exact test, respectively, according to actual data distribution.

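### Dose-response is a stated secondary objective, but neither the protocol nor the SAP prespecifies an estimate of the randomised 8 mg minus 4 mg difference for any efficacy endpoint

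*Protocol*

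**What the plan says.** **Objective.** Protocol 1.1, repeated in 3.2, has the secondary objective "To explore Pharmacokinetic and dose-response properties of SHR0302 in subjects with moderate to severe atopic dermatitis". The one endpoint beside it is "Systemic exposure of SHR0302 at steady state in subjects with atopic dermatitis (ie: concentration and area under the curve"), which measures exposure and not response. SAP 3.1.2 describes the objective as PK characteristics "and to explore the exposure-effect relationship".

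**Comparisons.** The hypotheses in protocol 9.1 and SAP 14.1 set each dose against placebo. The later sections keep to this:

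- SAP 14.2, primary: "The method of normal approximation to binomial will be used to test whether each active drug group is superior to the placebo group".
- SAP 14.1, everything else: "Analyses of secondary efficacy and other analyses will be provided for comparison 4 mg QD and 8 mg QD versus placebo, respectively".
- SAP 14.3.2, MMRM: "The comparisons of interest will be the contrasts between each active dose and placebo at every time point".

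The sensitivity analyses in SAP 14.4 vary the test, the analysis set and the handling of remote visits and missing data. They add no comparison between doses.

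**What is reported by arm.** SAP 14.2 gives the Week 12 IGA response rate with a 90% interval for each group, and SAP 14.4.1 adds Clopper-Pearson intervals. SAP 14.3 summarises the other endpoints by arm. The MMRM code in SAP 14.3.2 requests LS-mean differences without restricting them to comparisons with placebo.

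**PK.** Protocol 7.4 plans sampling for an exposure-response analysis. Protocol 9.4 plans population PK, with pharmacodynamic, efficacy and safety outcomes summarised by treatment group. SAP 5.2 adds: "The PK statistical analysis plan will not be included here as it will be described in a separate document".

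**The concern.** A randomised trial with two active doses can estimate without confounding how far those doses differ. The protocol names dose-response as something to explore, yet the plan never asks for that estimate. What the reader gets is two results against a shared placebo arm. If one is significant and the other is not, it is tempting to conclude that the doses differ. That does not follow, and the plan supplies no contrast or interval to check it. An exposure-response model cannot stand in for the contrast, because exposure varies between subjects on the same dose for reasons that randomisation does not control.

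**Working it through.** **Inputs.** Protocol 9.1: 44 randomised and 40 completers per arm; rates of 10% on placebo and 30% on each dose; Hochberg at two-sided 0.10; about 81% power. SAP 6: 35 per arm; 6%, 26% and 26%; same error control; about 82% power for at least one dose. The two sample sizes disagree, which is a separate matter; both are used here. Both documents assume equal rates for the two doses, so any gap between doses below is an assumption.

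**1. Reproduce the stated power.** I simulated 400,000 trials with two pooled-variance z-tests against a common placebo arm. Hochberg rejects both hypotheses if both p ≤ 0.10; otherwise it rejects the one with the smaller p if that p ≤ 0.05. The probability of at least one rejection is:

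- protocol, 40 per arm: 0.808 (stated about 81%);
- SAP, 35 per arm: 0.827 (stated about 82%).

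The trial is therefore sized to show that at least one dose differs from placebo.

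**2. Split results when the doses are identical.** P(exactly one dose significant) = P(at least one) − P(both).

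- SAP rates: 0.827 − 0.639 = 0.188.
- Protocol rates: 0.808 − 0.611 = 0.197.

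About one trial in five would show one dose significant and the other not, although the true rates are equal.

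**3. Precision of 8 mg minus 4 mg.** The 90% half-width is 1.645 × √[2p(1 − p)/n].

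- n = 35, p = 0.26: 1.645 × √(0.3848/35) = 0.172.
- n = 40, p = 0.30: 1.645 × √(0.42/40) = 0.169.
- n = 44, p = 0.30: 1.645 × √(0.42/44) = 0.161.

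**4. Power for 8 mg against 4 mg**, unadjusted, two-sided 0.10, with z = (d − 1.645·SE₀)/SE₁, where SE₀ is the pooled and SE₁ the unpooled standard error. For 26% against 36% at n = 35: SE₀ = √(2 × 0.31 × 0.69/35) = 0.1106, SE₁ = √[(0.1924 + 0.2304)/35] = 0.1099, z = (0.10 − 0.1819)/0.1099 = −0.745, power 23%.

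| Assumed gap | 35 per arm, 4 mg at 26% | 40 per arm, 4 mg at 30% |
|---|---|---|
| 10 points | 23% | 24% |
| 20 points | 54% | 57% |
| 30 points | 83% | 87% |

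Eighty per cent power for a 10-point gap would need 264 per arm (26% against 36%) or 281 per arm (30% against 40%).

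**5. Would a trend test do instead?** A Cochran-Armitage test over 0, 4 and 8 mg at two-sided 0.10 rejects in 72% of trials at 6/26/26% with 35 per arm, and in 70% at 10/30/30% with 40 per arm. The doses are equal in both cases, so the difference from placebo alone drives those rejections. Under an assumed graded response (6/16/26%, 35 per arm) it rejects in 77%, against 71% for at least one dose by Hochberg. The test can detect a drug effect, but it cannot tell 8 mg from 4 mg.

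**The case against.** The strongest reply is that a reader might infer that the trial will report nothing about 8 mg beside 4 mg, and that this is not so. Arm-level rates, intervals and summaries are planned. For binary endpoints a reader could derive the difference from them, and the MMRM code already prints the contrast. This reply stands against that stronger reading. It does not supply a prespecified estimate: two separate intervals are not the interval for the difference, SAP 14.3.2 names only the placebo contrasts as of interest, and the MMRM output does not cover IGA response. SAP 14.2 also bases descriptive summaries on non-missing data, so arm rates taken from those summaries may not have the denominators of the primary analysis.

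A reader might also infer that the SAP dropped a planned analysis without listing it in Table 2. The documents do not support this. Table 2 records changes to the analyses in the protocol, and protocol 9.2 never contained a dose-against-dose or trend analysis. What changed is the wording of an objective. Since that objective sits in the PK row with exposure as its endpoint, and protocol 7.4 itself speaks of exposure-response, the SAP wording may be meant as a clarification.

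The separate PK plan was not available, so the gap is shown for the protocol and this SAP only. It is also fair to say that protocol section 1 frames the trial as two doses compared with placebo, and that the trial is not sized for more. That argues for an exploratory label, not against an estimate.

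**Conclusion.** The point holds as a cheap improvement and not as a flaw in the primary analysis. Dose-response is a stated objective, the SAP words it differently, every named efficacy comparison is with placebo, and the randomised 8 mg minus 4 mg difference is not prespecified for any efficacy endpoint. Adding it would give an interval of about ±17 points under the planning rates (16.1 to 17.2 over the sample sizes in the documents). That is too wide to rank the doses unless they differ greatly, but it would stop a split result, expected in about one trial in five when the doses are equal, from being read as a dose effect. These figures rest on the planning rates and the normal approximation. The power figures rest also on assumed gaps between doses.

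**What to change.** 1. In SAP 14.1, add the 8 mg minus 4 mg difference with a 90% interval for Week 12 IGA response, Week 12 EASI75 and the MMRM endpoints. Label it exploratory and outside the Hochberg family.
2. Add ALPHA=0.1 to the LSMEANS statement in SAP 14.3.2. The DIFF option already yields the contrast, but the CL option alone gives 95% intervals. For the binary endpoints, run the SAP 14.2 code on the two active arms.
3. State that the interval for IGA response is expected to be about ±17 points and that the trial is not powered to separate the doses.
4. Align the objective wording in SAP 3.1.2 with protocol 1.1 and 3.2.
5. A trend test over 0, 4 and 8 mg is optional. If it is included, say that a difference between active treatment and placebo can drive it alone, and that it is not evidence that 8 mg differs from 4 mg.

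The cost is SAP wording and a few table columns, settled before unblinding. No new data are needed, and the sample size, primary test and error control do not change. The downside is a few more exploratory estimates, labelled as such.

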2.1 Background

Atopic dermatitis (AD), also known as atopic eczema, is a common chronic inflammatory skin disease characterized by recurrent attacks, pleomorphic skin lesions, dry skin, and severe pruritus. Atopic dermatitis usually begins in infancy or in children and is chronic, while severe cases may persit in adulthood. Meanwhile, some adult cases develop in adulthood. In most countries worldwide, the prevalence of atopic dermatitis is 10% - 20% in children and 2 - 8% in adults ¹. Moderate to severe atopic dermatitis has been reported in about 20% of cases ². In recent years, a large number of studies have shown a progressive increase in the prevalence of atopic dermatitis in both children and adults ⁵. In China, the prevalence of atopic dermatitis has also increased rapidly over 20 years³. In 2016, an epidemiological study conducted in 39 tertiary hospitals in 15 provinces showed that the overall prevalence of atopic dermatitis in China was $7.8\%^4$. Furthermore, it was reported that the incidence of atopic dermatitis in China after the age of 12 is also relatively common ⁶.

As a chronic relapsing disease, atopic dermatitis is not curable at present. The target of the treatment is to relieve or eliminate clinical symptoms, eliminate predisposing and/or aggravating factors, reduce and prevent relapses, and improve the quality of life of patients ³. Atopic dermatitis treatment depends on the extent and severity of the disease. Patients with mild atopic dermatitis may be treated with topical emollients, glucocorticoids, or calcineurin inhibitors⁷, patients with

moderate to severe disease often need to be treated with immunosuppressants or even biologics ⁸. Treatment for moderate to severe AD is difficult and often requires comprehensive therapies on an individualized basis. Topical glucocorticoids are considered as first-line therapy. However, they are not suitable for weak skin areas such as face, and long-term treatment would lead to local infections, atrophy, hirsutism, telangiectasia and other adverse reactions. Calcineurin inhibitors (such as tacrolimus, pimecrolimus cream) can be used on ace and other weak areas of the skin, but they also have irritation. Although systemic immunosuppressive agents (e.g., cyclosporine A, methotrexate, etc.) can also be used for the treatment of moderate to severe refractory AD, they also have many limitations. During treatment, it is necessary to monitor patient's blood pressure, renal function or liver function, etc. carefully⁹.

Recently, with the in-depth study of the pathogenesis of atopic dermatitis, more targeted and safer therapeutic method have become the research and development direction of AD treatment. Anti-IL-4/IL-13 monoclonal antibody Dupilumab (Dupixent *) approved by US Drug Administration in March 2017 and Received European Medicines Agency (EMA) in July 2017 provides an effective treatment for patients with moderate to severe atopic dermatitis in Europe and the United States who do not respond adequately to topical treatment or phototherapy ¹⁰, and avoids adverse effects of traditional hormones and immunosuppressive agents (e.g., cyclosporine A, methotrexate). However, a large number of studies have shown that although biologics are effective and well tolerated, long-term treatment may result in the absence of responses caused by immunogenicity in some patients. Therefore, patients may need to increase the dose and/or decrease the dosing interval. In addition, most patients cannot afford these higher-priced biologics.

